The advantage to a retrospective medical record review approach over a database analysis is that of being designed specifically to collect data that fulfils the study objectives. Thus, it readily collects and informs on all key drug related clinical outcome measures of critical importance to this study, in a consistent manner, across countries. The resulting data set enables direct comparisons across markets, delivering in turn greater confidence in the reliability of conclusions drawn from the research. An additional advantage of this approach lies in the ability to obtain information that only the treating physician may be aware of, such as the reasons for treatment switches or discontinuations or more perceptive questions that rely on the physicians' professional opinion.

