### 9.3 Variables

**Table 1. List of Study Variables**

Variable	Role	Data Source(s)	Operational Definition
Patient demographics	Baseline Sub-group identifier	Patient records	Age, ethnicity, weight, height, biomarker status, family history of breast cancer.
Clinical characteristics	Baseline Sub-group identifier	Patient records	Time since diagnosis, staging, node status, menopause status. ECOG/Karnofsky functional status, diagnosis for which palbociclib combination was prescribed, sites of metastases, de novo vs. recurrent disease.
Comorbid conditions	Baseline Sub-group identifier	Patient records	Comorbid conditions.
Early treatment history	Baseline Sub-group identifier	Patient records	Adjuvant treatments received since breast cancer diagnosis, time since end of adjuvant treatment, surgery/radiotherapy received.
Advanced treatment history	Baseline Sub-group identifier	Patient records	Treatments and supportive therapies received since metastatic/advanced HR+/HER2- diagnosis, duration of treatments, reasons for regimen changes.
Palbociclib combination treatment	Exposure Sub-group identifier	Patient records	Starting dose, duration of treatment, line of treatment, changes in dose, interruptions, cycle delays and discontinuations; where possible reasons for change in treatment.
Clinical outcomes	Outcomes	Patient records	Proportion progression free, ORR, TTP, PFS, patient death, 1-year and 2-year survival in all patients and within specific subgroups.

PFIZER CONFIDENTIAL

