2.2 STUDY OBJECTIVES

Primary Objectives:

1. To describe the demographics and clinical characteristics of patients who have received palbociclib combination with aromatase inhibitor (as prescribed by the Physician) in menopausal state as initial endocrine therapy in MBC or with fulvestrant after progression on prior endocrine therapy.
2. To summarize adjuvant therapies received for the treatment of early or locally advanced breast cancer (Stages 0-IIIa).
3. To describe treatments received in the advanced/metastatic setting, before and after palbociclib combination use.
4. To describe dosing and dose changes, interruptions, delays, and discontinuations associated with palbociclib use in clinical practice.
5. To describe supportive therapies received by patients while receiving palbociclib combination treatments.
6. To determine in overall population and defined subgroups, clinical outcomes including (but not limited to):
 - Proportion of patients who are progression free at specific intervals (eg, 6, 12, 18 months).
 - Objective response rate (ORR) - depending on availability of follow-up data.
 - Proportion of alive patients 1 and 2 years post palbociclib combination initiation -depending on availability of follow-up data (sample size permitting).

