7.2 STATISTICAL ANALYSES

- **Demographic Characteristics**

The demographic and baseline characteristics will be summarized by using descriptive statistics. Continuous variables such as age will be summarized by number of observations (n), arithmetic mean (mean), standard deviation (SD), median, minimum value (min), and maximum value (max) and Categorical variables such as menopausal status, induced menopause, family history of breast cancer and patient deceased will be presented by frequency (n) and percentage (%).

- **Initial and advance breast cancer diagnosis**

For all the patients initial diagnosis of breast cancer stages (stage 0 to stage IV) will be presented in frequency counts (n) and percentage (%). For the advance stages (stage IIIb, IIIc or IV) of breast cancer patients again locoregionally advanced or metastatic frequency counts (n) and percentage (%) will be given. For the metastatic disease, sites of metastases such as Bone, Liver, Brain, Lung, Lymph nodes and others with further segregation like single or multiple locations will be presented in frequency (n) and percentage (%).

- **Prior Therapy**

For all patient's prior therapy type (Targeted, Endocrine and Chemotherapy) will be presented by frequency count and percentage

- **Performance status**

Performance status using ECOG scale at the initiation of palbociclib treatment. Status is measured using 4 point scale from fully active to completely disable and will be summarized by frequency (n) and percentage (%).

- **Early Breast Cancer Treatment History**

Following early breast cancer diagnosis treatments received such as surgery, radiotherapy, neoadjuvant treatment, adjuvant chemotherapy, adjuvant endocrine therapy by patients will be summarized by frequency (n) and percentage (%).

- **Palbociclib Treatment**

PFIZER CONFIDENTIAL

For all the patients initial dose prescribed of palbociclib, any dose adjustments made to palbociclib and for each dose adjustment if dose reduced or increased, palbociclib was temporarily interrupted, cycle delay and reason for dose change will be summarized by frequency (n) and percentage (%). Moreover, complete summary (frequency and percentage) of all supportive therapies that patients received will be presented.

- **Advance Breast Cancer Treatment History**

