Table 3.1 Advance Breast Cancer Diagnosis by line of treatment (first line vs. second and later line)

Table 4 Prior Therapy– All Subjects

PFIZER CONFIDENTIAL

Characteristic (Unit)	Statistics	Palbociclib (N=xx)
Prior Therapy		
Targeted	n (%)	xx (xx.x)
Endocrine	n (%)	xx (xx.x)
Chemotherapy	n (%)	xx (xx.x)
Abbreviations: N = number of subjects in Palbociclib group; n = number of subjects in specified category		
Note 1: Percentages are based on the number of subjects in the Palbociclib group.		
Table 4.1 Prior Therapy by line of treatment (first line vs. second and later line)		

Table 5 Performance Status– All Subjects

PFIZER CONFIDENTIAL

Characteristic (Unit)	Statistics	Palbociclib (N=xx)
Performance Status on ECOG Scale at Palbociclib initiation		
0	n (%)	xx (xx.x)
1	n (%)	xx (xx.x)
2	n (%)	xx (xx.x)
3	n (%)	xx (xx.x)
4	n (%)	xx (xx.x)
5	n (%)	xx (xx.x)
Abbreviations: N = number of subjects in Palbociclib group; n = number of subjects in specified category; ECOG = Eastern Cooperative Oncology Group		
Note 1: Percentages are based on the number of subjects in the Palbociclib group.		
Table 5.1 Performance Status by line of treatment (first line vs. second and later line)		

PFIZER CONFIDENTIAL

Table 6 Early Breast Cancer Treatment History – All Subjects

Characteristic (Unit)	Statistics	Palbociclib (N=xx)
Neo/Adjuvant Therapy Received by Patient		
Adjuvant chemotherapy	n (%)	xx (xx.x)
Adjuvant endocrine therapy	n (%)	xx (xx.x)
Neoadjuvant treatment	n (%)	xx (xx.x)
Radiotherapy	n (%)	xx (xx.x)
Surgery	n (%)	xx (xx.x)
Don't Know	n (%)	xx (xx.x)
Abbreviations: N = number of subjects in Palbociclib group; n = number of subjects in specified category		
Note 1: Percentages are based on the number of subjects in the Palbociclib group.		
Table 6.1 Early Breast Cancer Treatment History by line of treatment (first line vs. second and later line)		

PFIZER CONFIDENTIAL

Table 7 Palbociclib Treatment – All Subjects

Characteristic (Unit)	Statistics	Palbociclib (N=xx)
Initial Dose Prescribed		
125 mg/day	n (%)	xx (xx.x)
100 mg/day	n (%)	xx (xx.x)
75 mg/day	n (%)	xx (xx.x)
Dose Adjustment		
No	n (%)	xx (xx.x)
Yes	n (%)	xx (xx.x)
Reason for Dose Adjustment		
Side effects/toxicity	n (%)	xx (xx.x)
Lack of response	n (%)	xx (xx.x)
Patient request	n (%)	xx (xx.x)
Other reasons	n (%)	xx (xx.x)
Abbreviations: N = number of subjects in Palbociclib group; n = number of subjects in specified category		

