Note 1: Percentages are based on the number of subjects in the Palbociclib group.		
Table 7.1 Palbociclib Treatment by line of treatment (first line vs. second and later line)		

PFIZER CONFIDENTIAL

Table 8 Dose Adjustment – All Subjects

Characteristic (Unit)	Statistics	Palbociclib (N=xx)
Dose Reduced		
Yes	n (%)	xx (xx.x)
Dose Resumed following interruption or cycle delay		
Yes	n (%)	xx (xx.x)
Dose Interrupted (temporarily stopped during a dose cycle)		
Yes	n (%)	xx (xx.x)
Cycle delay (the next cycle is pushed back)		
Yes	n (%)	xx (xx.x)
Combination partner therapy continued		
Yes	n (%)	xx (xx.x)
Abbreviations: N = number of subjects in Palbociclib group; n = number of subjects in specified category		
Note 1: Percentages are based on the number of subjects in the Palbociclib group.		
Table 8.1 Dose Adjustment by line of treatment (first line vs. second and later line)		

PFIZER CONFIDENTIAL

Table 9 Palbociclib Treatment- Supportive Therapies – All Subjects

Characteristic (Unit)	Statistics	Palbociclib (N=xx)
Supportive therapies		
Nutritional Support	n (%)	xx (xx.x)
Bisphosphonates	n (%)	xx (xx.x)
Antibiotics	n (%)	xx (xx.x)
Anti-anxiety drugs	n (%)	xx (xx.x)
Opioid extended release	n (%)	xx (xx.x)
NSAIDs	n (%)	xx (xx.x)
-----	-----	-----
-----	-----	-----
-----	-----	-----
Don't Know	n (%)	xx (xx.x)
Abbreviations: N = number of subjects in Palbociclib group; n = number of subjects in specified category		
Note 1: Percentages are based on the number of subjects in the Palbociclib group.		
Table 9.1 Palbociclib Treatment- Supportive Therapies by line of treatment (first line vs. second and later line)		

PFIZER CONFIDENTIAL

Table 10 Advance Breast Cancer Treatment History – All Subjects

Characteristic (Unit)	Statistics	Palbociclib (N=xx)
Time duration from Diagnosis to initiation of Palbociclib	n	xx
	Mean (SD)	xx.x (xx.xx)
	Median	xx.x
	Min, Max	xx, xx
Line of treatment		
1st line	n (%)	xx (xx.x)
2nd line	n (%)	xx (xx.x)
3rd line	n (%)	xx (xx.x)
4th or later line	n (%)	xx (xx.x)
Abbreviations: N = number of subjects in Palbociclib group; n = number of subjects in specified category		
Note 1: Percentages are based on the number of subjects in the Palbociclib group.		
Table 10.1 Advance Breast Cancer Treatment History by line of treatment (first line vs. second and later line)		

PFIZER CONFIDENTIAL

Table 11 Clinical Outcome – All Subjects

Characteristic (Unit)	Statistics	Palbociclib (N=xx)
Complete response		
Yes	n (%)	xx (xx.x)
Partial response		

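### Primary objective 4 covers discontinuations, but the visible SAP palbociclib paragraph and Tables 7 and 8 report neither permanent stopping, its reason, nor time on palbociclib

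*SAP*

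**What the plan says.** Objective 4 has the same wording in protocol section 8 and SAP 2.2: "To describe dosing and dose changes, interruptions, delays, and discontinuations associated with palbociclib use in clinical practice". Protocol Table 1 defines the palbociclib exposure variable as "Starting dose, duration of treatment, line of treatment, changes in dose, interruptions, cycle delays and discontinuations; where possible reasons for change in treatment". Protocol 9.1 also defends chart review on the ground that it can recover facts known only to the treating physician, "such as the reasons for treatment switches or discontinuations".

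The SAP 7.2 paragraph on palbociclib treatment covers the initial dose, then "any dose adjustments made to palbociclib and for each dose adjustment if dose reduced or increased", then "palbociclib was temporarily interrupted, cycle delay and reason for dose change will be summarized by frequency (n) and percentage", and finally supportive therapies.

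In SAP Appendix 1, the Table 7 shell has the initial dose, whether any adjustment was made, and "Reason for Dose Adjustment". The Table 8 shell has dose reduction, resumption, temporary interruption, cycle delay, and "Combination partner therapy continued". Table 10 has one duration, from diagnosis to the start of palbociclib, and the line of treatment.

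**The concern.** The objective names five things, and the fifth has no visible place in the outputs meant for palbociclib exposure. If Tables 7 and 8 are programmed as drawn, they will not show how many patients stopped palbociclib for good, why, or after how long. Stopping for toxicity could not be told apart from stopping for progression. Treatment patterns are in the study title, and recovering reasons for discontinuation is one of the protocol's own arguments for the design, so a reader of the report would look for these results.

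**Working it through.** This is a check of coverage. The documents give no figure to reproduce, because the study is descriptive and states no sample-size calculation.

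**Step 1. Set the commitments beside the visible outputs.**

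| Item | Source | SAP 7.2 palbociclib paragraph | Tables 7 and 8 |
|---|---|---|---|
| Dosing | Objective 4 | Initial dose | Table 7 |
| Dose changes | Objective 4 | Reduced or increased, with reason | Table 7 (any adjustment, reason), Table 8 (reduced) |
| Interruptions | Objective 4 | Temporary interruption | Table 8 (interruption, resumption) |
| Delays | Objective 4 | Cycle delay | Table 8 |
| Discontinuations | Objective 4 and protocol Table 1 | None | None |
| Duration of treatment | Protocol Table 1 only | None | None |

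Four of the five items in objective 4 are covered.

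**Step 2. Ask whether an existing row could stand in for discontinuation.**

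- The interruption row in Table 8 is defined as a temporary stop within a cycle.
- The resumption row tabulates only a yes count. A patient can also stop for good without any earlier interruption or delay, so non-resumption is not a proxy.
- The Table 7 reasons are reasons for a dose adjustment. The categories are toxicity, lack of response, patient request and other. Progression and death are not among them.
- The partner-therapy row describes the other drug.
- The duration in Table 10 ends where palbociclib exposure begins.

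**Step 3. Ask whether another visible table covers it.** SAP section 8 lists Tables 1 to 11 with their by-line versions. No title refers to discontinuation or time on treatment.

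**Step 4. Show why a bare percentage would not be enough.** Minimum follow-up is 6 months with an aromatase inhibitor and 3 months with fulvestrant (protocol 9.2.1). The longest possible follow-up also differs by partner. The protocol's example index date for the aromatase inhibitor is 26 December 2016 and data collection is planned to end in January 2021, which is about 4 years. Fulvestrant use was approved in India in December 2017, which gives about 3 years at most.

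For illustration, assume exponential stopping with the progression-free medians quoted in protocol section 7 (24.8 months with letrozole, 9.5 months with fulvestrant). The 24-month point is chosen for comparison. The share stopped by month t with median m is 1 − exp(−ln 2 × t / m):

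- m = 24.8, t = 6: 1 − exp(−0.693 × 6/24.8) = 15.4%
- m = 24.8, t = 24: 1 − exp(−0.693 × 24/24.8) = 48.9%
- m = 9.5, t = 3: 1 − exp(−0.693 × 3/9.5) = 19.7%
- m = 9.5, t = 24: 1 − exp(−0.693 × 24/9.5) = 82.6%

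Within each partner the stopping rate is constant, so the differences come from follow-up alone.

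**The case against.** The strongest objection is redaction. Blocks are removed after the SAP text on advanced treatment history, which governs Table 10, after the clinical-outcome text, in and after Tables 11 and 11.1, and in protocol 9.7. Discontinuation or treatment duration could be reported in any of them, and objective 4 does not say which table must answer it. This stands. A reader might infer that the SAP reports discontinuation nowhere, and the documents do not support that.

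Other objections also stand in part:

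- A reader might take time on treatment to be part of objective 4. It is not named there and comes only from protocol Table 1.
- The exposure outputs are not confined to reductions, interruptions and delays. They also cover initial dose, increases, reasons for adjustment, resumption and partner continuation. None of these captures permanent stopping.
- The exponential figures use progression-free medians in place of stopping times, and they test a crude row that the SAP does not propose. Patients are selected forward from an early index date, so many may have follow-up well above the minimum. The figures illustrate dependence on follow-up and do not forecast this study.
- Protocol Table 1 lists starting dose but does not itemise a start date, and it plans reasons only where possible. The case report form is not available here, so its coding of discontinuation reasons cannot be checked.
- The objective is to describe. A cumulative incidence of toxicity-related stopping and a further split by partner go beyond what it needs. At the planned 7:3 ratio there would be about 0.3 × 150 = 45 later-line patients.

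**Conclusion.** The point holds for the visible exposure outputs. The SAP palbociclib paragraph and Tables 7 and 8 leave out one of the five items in a primary objective (discontinuation, with its reason) and one exposure variable planned in protocol Table 1 (duration of treatment).

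This rests on reading the paragraph and those two shells as complete, since neither shows redaction. It does not rest on any claim about the redacted sections. If one of them already reports these items, what remains is a missing cross-reference. The gap is worth closing because the change is small and the variables are already planned.

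**What to change.** Add to Tables 7 and 7.1, overall and by line of treatment:

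- number and percentage of patients who permanently discontinued palbociclib;
- the recorded reason: progression, toxicity, patient request, death, other, unknown;
- time on palbociclib by the Kaplan-Meier method that protocol 9.7 already gives for time-to-event variables, with patients still on treatment at data collection censored.

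Name the same items in the SAP 7.2 palbociclib paragraph, and state there the start, event and censoring dates. If a redacted section already reports them, cross-refer to it from that paragraph instead. Cumulative incidence of toxicity-related stopping and a split by partner drug are optional.

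The cost is a few sentences of SAP text and some table rows. Discontinuations, duration and, where possible, reasons are planned variables. A palbociclib start date is not itemised in protocol Table 1, but the Table 10 interval and the minimum follow-up criterion both need one. Before finalising the rows, check that the case report form distinguishes permanent from temporary stopping and how it codes the reason.

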#### Patient inclusion criteria

Patients must meet all of the following inclusion criteria to be eligible for inclusion in the study:

- $\geq 18$  years old females.
- HR+/HER2- breast cancer diagnosis with confirmed metastatic or advanced disease.
- Received palbociclib with aromatase inhibitor (as prescribed by the Physician) as initial endocrine therapy in postmenopausal MBC patients or with fulvestrant in patients who have progressed on prior endocrine therapy

- Patients on LHRH agonists for ovarian function suppression in pre- or perimenopausal stage only if prescribed palbociclib with fulvestrant.
- No prior or current enrolment in an interventional clinical trial for ABC/MBC.
- Minimum of 3 months of follow up data since palbociclib with fulvestrant initiation, or minimum of 6 months of follow up data since palbociclib with aromatase inhibitor initiation.

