5 ENDPOINTS AND COVARIATES**5.1 EFFICACY/EFFECTIVENESS ENDPOINT(S)**

- Treatment success of the patients treated with palbociclib with aromatase inhibitor (as prescribed by the Physician) will be progression free i.e. complete response, partial response or stable disease at the end of regimen.

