For all the patients' line of treatment for Palbociclib combination started will be given in frequency and percentage, time (months) from diagnosis of breast cancer to start of Palbociclib combination will be presented as mean, median, standard deviation and range value (minimum and maximum). **CCI**

CCI

[figure not shown]
- **Clinical Outcome**

For all the patients initially recorded responses like complete positive response to the disease, partial positive response to the disease, stable disease and progressive disease, will be summarized with frequency counts (n) and percentages (%). Moreover, based on initial response, objective response rate (ORR) and clinical benefit rate (CBR) will be calculated and presented as percentage.

CCI

PFIZER CONFIDENTIAL

PFIZER CONFIDENTIAL

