Yes	n (%)	xx (xx.x)
Stable disease		
Yes	n (%)	xx (xx.x)
Progressive disease		
Yes	n (%)	xx (xx.x)
Objective Response Rate (ORR)		
Yes	n (%)	xx (xx.x)
Clinical Benefit Rate (CBR)		
Yes	n (%)	xx (xx.x)

CCI

Abbreviations: N = number of subjects in Palbociclib group; n = number of subjects in specified category

[figure not shown]
Note 1: Percentages are based on the number of subjects in the Palbociclib group.

PFIZER CONFIDENTIAL

Table 11.1 Clinical Outcome by line of treatment (first line vs. second and later line)

A large black rectangular redaction box covers the majority of the page content below the table caption. Within this redaction, the letters 'CCI' are printed in large, bold, red font, likely representing the first few letters of the table title.

CCI

A horizontal black redaction bar is located at the bottom of the page, obscuring the bottom portion of the page content.

PFIZER CONFIDENTIAL

PFIZER CONFIDENTIAL

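### The SAP takes CBR from the first recorded response alone, so stable disease counts as clinical benefit however soon progression follows

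*SAP*

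**What the plan says.** Under Clinical Outcome, SAP 7.2 tabulates the first recorded category (complete response, partial response, stable disease or progressive disease): "For all the patients initially recorded responses like complete positive response to the disease". It then derives both rates from that category: "Moreover, based on initial response, objective response rate (ORR) and clinical benefit rate (CBR) will be calculated and presented as percentage". The Table 11 shell gives CBR one row with a count and percentage, and Table 11.1 repeats the table by line of treatment. The shell's note on denominators reads: "Percentages are based on the number of subjects in the Palbociclib group".

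No visible text in either document lists the components of CBR, sets a minimum duration for stable disease, or says when the first assessment takes place. The visible protocol does not mention CBR.

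Three other places bear on the point:
- SAP 5.1 defines treatment success as "complete response, partial response or stable disease at the end of regimen". That is a similar grouping at a different time, and it is not linked to CBR.
- The protocol's patient inclusion criteria require "Minimum of 3 months of follow up data since palbociclib with fulvestrant initiation", or a "minimum of 6 months of follow up data since palbociclib with aromatase inhibitor initiation".
- Protocol 9.3 (Table 1) lists TTP, PFS and death as outcomes, and Protocol 9.7 plans Kaplan-Meier description of time to progression.

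**The concern.** A row labelled clinical benefit invites the reader to assume that stable disease lasted. Under the SAP's rule, a patient stable at a first assessment in month 3 who progresses in month 4 counts the same as one who stays stable for a year. Moving from first to best recorded response would not change this, because one stable reading would still qualify. The point is therefore separate from the question of whether ORR should use the first response.

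In a descriptive study the label and its definition are what the reader takes away. Protocol section 7 says the results should help to inform treatment decisions.

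**Working it through.** The plan states no CBR value, assumed rate or precision target, so there is no figure to reproduce. The check has a logical part and an illustration of size.

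**1. Direction.** Let N be all subjects, and let CR, PR and SD be counts of first recorded responses. Let s be the number with first-recorded SD who progress or die before the duration threshold.
- CBR as planned (composition inferred) = (CR + PR + SD) / N.
- CBR with a duration rule on SD = (CR + PR + SD − s) / N.
- Difference = s / N, which is never negative.

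Patients with SD whose follow-up ends before the threshold are a further group that the duration rule cannot classify. They need their own row.

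**2. Relation to the PD row.** With U patients whose response is unknown, CBR% = 100 − PD% − U%. Table 11 divides by all subjects, SAP 7.1 allows a missing category, and Protocol 9.8 accepts unknown as an eCRF answer. U need not be zero.

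**3. Size (illustration only).** Inputs from the documents:
- Median PFS 24.8 months with letrozole and 9.5 months with fulvestrant (Protocol section 7).
- First line to later line about 7:3 (Protocol 9.1).
- About 150 patients (Protocol 9.5).

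Assumptions not in the documents:
- Exponential progression, S(t) = 0.5^(t / median).
- One common first-assessment time of 2, 3 or 4 months.
- A 24-week threshold, which is 168 / 30.44 = 5.52 months.
- Line of treatment as a proxy for regimen.

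At 24 weeks:
- AI: 0.5^(5.52/24.8) = 0.857.
- Fulvestrant: 0.5^(5.52/9.5) = 0.668.
- Mix: 0.7 × 0.857 + 0.3 × 0.668 = 0.800.

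At 3 months:
- AI: 0.5^(3/24.8) = 0.920.
- Fulvestrant: 0.5^(3/9.5) = 0.803.
- Mix: 0.7 × 0.920 + 0.3 × 0.803 = 0.885.

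The gap at 3 months is 0.084 from unrounded values, and 0.084 × 150 is about 12.6 patients. Other assessment times, same method:

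| First assessment | AI | Fulvestrant | 7:3 mix | Mix minus 24-week value | Of 150 |
|---|---|---|---|---|---|
| 2 months | 0.946 | 0.864 | 0.921 | 12.1 points | 18.1 |
| 3 months | 0.920 | 0.803 | 0.885 | 8.4 points | 12.6 |
| 4 months | 0.894 | 0.747 | 0.850 | 5.0 points | 7.4 |

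With a 6-month threshold instead, the mix at the threshold is 0.786 and the gaps are 13.6, 9.9 and 6.4 points.

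**4. Why each gap is a ceiling for its own assessment time.** It counts everyone who progresses between the first assessment and the threshold. Only those whose first response was SD contribute to s. Early-progressing responders still count as benefit under both definitions, and patients with no recorded response count as non-benefit under both. The share with SD is not given.

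**The case against.** The strongest reply is that a duration rule comes from outside. Neither document defines CBR or mentions 24 weeks, so a claim of overstatement is relative to a definition the sponsor never adopted. Redacted text also follows both the sentence in SAP 7.2 and the CBR row in Table 11, and a list of components could sit there. CBR is not a protocol objective. Non-progression over time already has its own objective (progression-free at 6, 12 and 18 months), and the study has no hypotheses or decision rules.

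Much of this stands. The composition is inferred, the threshold is an assumption, and the consequence is confined to interpretation. It does not remove the point. The visible sentence states a working rule, and any hidden duration condition would contradict it.

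Some stronger readings are tempting but unsupported:
- *A reader might infer that the CBR row simply repeats the complement of the PD row.* That is true only if every patient has a recorded response, and the plan allows for unknown ones.
- *A reader might infer that the contrast between lines is compressed.* In the illustration the AI–fulvestrant gap is 11.7 points at 3 months (0.920 − 0.803) and 18.9 at 24 weeks (0.857 − 0.668). Line is not regimen, however: fulvestrant eligibility requires progression on prior endocrine therapy, with no restriction to the metastatic setting. The SD share by line is also unknown. Compression is a possibility only.
- *A reader might infer that lasting stable disease cannot be observed in the fulvestrant group.* Three months is a floor. Physicians start from 60 days after their first prescription and select consecutively. Protocol section 7 dates the Indian fulvestrant approval to December 2017, and data collection was planned from November 2020. Few patients should have short follow-up.

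**Conclusion.** The point holds. As written, the plan yields at most disease control at the first recorded assessment under a clinical benefit label. If CBR is CR + PR + SD, it cannot be lower than a version that adds a duration condition to SD on the same denominator.

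The excess is at most about 5 points (first assessment at 4 months) to 12 points (at 2 months), and 8 points at 3 months. These figures rest on exponential progression, trial medians carried over to routine practice, the 7:3 line split standing in for regimen, and a 24-week rule. They should not be read as an estimate of the actual overstatement.

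The change is worth making because it is cheap and the label misleads. No test or decision depends on the row.

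**What to change.** In SAP 7.2 and Tables 11 and 11.1, do one of the following.

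**Relabel.** Keep the calculation and call the row *disease control (CR + PR + SD) at first recorded assessment*, with the components stated. This costs only wording.

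**Redefine.** Define CBR as recorded CR or PR, or SD without progression or death for a stated minimum duration (for example 24 weeks) from palbociclib start. Say whether CR and PR are first or best recorded. Then:
- Keep all subjects in the denominator.
- Show SD with follow-up shorter than the threshold, and unknown response, as separate rows. Removing only the short-follow-up SD patients would make exclusion depend on outcome.
- Add a sensitivity line restricted to patients who started palbociclib at least that duration before data collection, whatever their response.

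Under either option, say how the row relates to the end-of-regimen treatment success in SAP 5.1.

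The cost of redefining is SAP wording, one derived variable, two extra rows and one sensitivity line. It uses the progression and death dates that the planned PFS analysis needs. That these dates are captured is inferred from the planned analyses, since the CRF is not among the documents. The aromatase inhibitor entry rule (6 months) already exceeds 24 weeks, so short follow-up should arise mainly in fulvestrant patients. With first-recorded categories kept, the reported CBR would be the same or lower.
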